**Table 7. Probability of observing the number (%) of subjects with DLT out of a cohort of 6 subjects**

Observed number (%) of subjects with DLT	Probability (p-value) under different assumptions				
	$\theta_0 = 0.20$	$\theta_0 = 0.25$	$\theta_0 = 0.30$	$\theta_0 = 0.35$	$\theta_0 = 0.40$
0 (0%)	0.74	0.82	0.88	0.92	0.95
1 (17%)	0.34	0.47	0.58	0.68	0.77
2 (34%)	0.099	0.17	0.26	0.35	0.46
3 (50%)	0.017	0.038	0.07	0.12	0.18

Through this procedure, the MTD of trigriluzole in combination with nivolumab will be identified. The MTD will then be tested in combination with pembrolizumab using the same escalate/de-escalate/stay rules.

### Dose Limiting Toxicity

#### Definition of DLT

The occurrence of any Grade 3 or higher toxicity during the DLT evaluation period (i.e., occurred during the first 4 weeks of therapy) will be considered a DLT, if judged by the treating investigator to be related to the administration of either study drug or the combination of study drugs.

**EXCEPTION:** Grade 3 amylase or lipase elevation without clinical symptomatology of pancreatitis (i.e. no epigastric pain and vomiting) will not be considered a DLT and does not require SAE reporting.

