### **1.3 Research Design and Methods**

**All visits are relative to the treatment start date, Day -14. If a treatment visit is delayed, the next visit will still occur on time relative to the initial start date (e.g. If Week 3 occurs 7 days late, Week 5 will still occur at Week 5).**

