##### **Anti-PD-1 antibody (pembrolizumab or nivolumab)**

PD-1 inhibitor treatment will consist of either nivolumab or pembrolizumab. PD-1 inhibitor will begin at Week 1 (following 14 day lead-in with trigriluzole). Subsequent PD-1 inhibitor treatments will occur at 2-3-week intervals, depending on the schedule of the PD-1 inhibitor as per the Study Calendar.

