##### **Treatment Assignment**

Dose escalation of trigriluzole with nivolumab will proceed up to a maximum of 280 mg PO BID to identify the MTD. Subjects will be enrolled on the trial starting with Cohort 1 (Table 3) in a starting cohort size of 3 subjects. Subjects will be followed for 4 weeks to observe for dose-limiting toxicity (DLT). The decision to escalate or deescalate to a new dosing cohort or

to expand a dosing cohort will be made using the procedure described in the statistical analysis section.

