### **1.7.6 Treatment Administration**

#### **Trigriluzole Administration**

Trigriluzole will be self-administered by the patient. Trigriluzole will be first administered in the clinic setting. Trigriluzole can be taken without regards to meals (on a full stomach or an empty stomach). Morning or evening administration is acceptable for once daily dosing. No weight-based dosing calculation is necessary as trigriluzole is administered using flat dosing.

**Lead-in period.** Subjects will begin therapy with continuous oral dosing of trigriluzole for a lead-in period of 14 days (Week -2, Day -14 to Week -1, Day -1). Day -1 is followed by Day 1 (There is no Day 0 or Week 0).

**Combination treatment.** At the start of Week 1, subjects will continue oral dosing of trigriluzole and begin therapy with PD-1 inhibitor. On the days of IV treatment visits, there is no window for administration of trigriluzole with respect to the PD-1 inhibitor.

**Compliance/adherence assessment.** Subjects will be *strongly encouraged* to use the Pill Diaries that are provided by the study. If a patient reports compliance <80% of days, they should be re-educated by the research nurse and/or treating investigator on instructions for dosing trigriluzole at home.

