### **DLT observation period**

There will be a 5-week evaluation period for observation of DLT during which time new subjects may be accrued within the same dose cohort, but dose escalation or de-escalation beyond the current dose cohort shall not be allowed. The date of reference for the 5 weeks is the first day of treatment including the lead-in period (Day -14); therefore the end of the DLT observation period occurs at Week 3. The end of the DLT observation period will not coincide with an office visit in the pembrolizumab cohorts; if no DLT has been reported by that time, the evaluation period will be considered to be passed.

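### The DLT window is 4 weeks in two sections and 5 weeks in a third, so a related Grade 3+ event on Days 15 to 21 may or may not count as a DLT

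*Combined protocol and SAP*

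**What the plan says.** Three places in the combined protocol and SAP set the DLT window.

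- Section 1.7.5.1, Treatment Assignment: "Subjects will be followed for 4 weeks to observe for dose-limiting toxicity (DLT". That sentence names no start date.
- Section 6.1, Definition of DLT, which requires a related toxicity of Grade 3 or higher: "i.e., occurred during the first 4 weeks of therapy) will be considered a DLT".
- Section 6.1, DLT observation period: "There will be a 5-week evaluation period for observation of DLT". It counts from Day -14 with the lead-in included, forbids a change of dose level while the period runs, and concludes: "therefore the end of the DLT observation period occurs at Week 3". It adds: "The end of the DLT observation period will not coincide with an office visit in the pembrolizumab cohorts".

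The day numbering comes from elsewhere. Section 1.3 sets Day -14 as the treatment start. Section 1.7.6 says "Day -1 is followed by Day 1 (There is no Day 0 or Week 0". Section 1.7.5.1 says "PD-1 inhibitor will begin at Week 1 (following 14 day lead-in with trigriluzole". The calendars in section 1.10 place nivolumab visits at Weeks 1, 3 and 5 and pembrolizumab visits at Weeks 1, 4 and 7.

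The replacement rule in section 6.1, Missing data, relies on the same observation period and gives no length of its own.

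**The concern.** The number of DLTs is the input to Table 6. Table 6 drives escalation, and escalation yields the MTD/RP2D, which is the primary endpoint. A rule for which events count should have one length, and this one has two. No choice of start date reconciles them: the definition counts from the start of therapy, section 1.3 puts that start at Day -14, and the 5-week period counts from Day -14 as well.

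On the literal 5-week reading, two investigators who both follow the protocol could classify the same Day 18 event differently. The disputed days also include the time just after the second nivolumab dose (nominal Day 15), when a combination toxicity would be of particular interest.

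**Working it through.** **Day count.** Day -14 is the first day of treatment and there is no Day 0, so the lead-in supplies 14 days.

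- 4 weeks = 28 days = 14 lead-in + 14, so the last day is Day 14 (end of Week 2).
- 5 weeks = 35 days = 14 lead-in + 21, so the last day is Day 21 (end of Week 3).

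The plan's own figure reproduces: Weeks -2, -1, 1, 2 and 3 make five weeks and end with Week 3. The disputed span is Days 15 to 21, which is 35 - 28 = 7 days.

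**Second reading of Week 3.** Section 1.3 uses week numbers as visit names ("If Week 3 occurs 7 days late, Week 5 will still occur at Week 5"). The nominal Week 3 visit is on Day 15, after 28 full days. The remark that the end misses a visit under pembrolizumab fits a visit-based end under nivolumab. A window through Day 15 has 14 + 15 = 29 days, so the gap to the 4-week window is 29 - 28 = 1 day, and the 5-week label would be the mistake.

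**Effect on the decision.** Table 6 as printed gives, for three patients, 0 = Escalate, 1 = Stay, 2 = De-escalate, 3 = De-escalate. Because the table text may be damaged, I recomputed the first three entries by mTPI with the stated target of 0.30 and margins of 0.05, assuming a uniform prior. Unit probability mass below / inside / above 0.25 to 0.35:

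| DLTs | Below | Inside | Above | Action |
|---|---|---|---|---|
| 0/3 | 2.73 | 1.38 | 0.27 | Escalate |
| 1/3 | 1.05 | 1.75 | 0.87 | Stay |
| 2/3 | 0.20 | 0.76 | 1.34 | De-escalate |

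One extra DLT therefore changes the action at 0/3 to 1/3 and at 1/3 to 2/3. From 2/3 to 3/3 the printed action stays the same.

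**Illustration of size (assumed inputs).** Let p be the DLT probability over the longer window of L days, and q the part captured by Day 14. Two hazard shapes are assumed:

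- constant from Day -14: q = 1 - (1 - p)^(28/L), with L = 35 or 29;
- acting on combination days only: q = 1 - (1 - p)^(14/M), with M = 21 or 15.

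The actions differ when there are 0 early DLTs and at least 1 late one, or 1 early and at least 1 late:

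P(differ) = [(1 - q)^3 - (1 - p)^3] + 3q[(1 - q)^2 - (1 - p)^2].

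Example: p = 0.30, constant hazard, L = 35. Then q = 1 - 0.70^0.8 = 0.248. The first term is 0.425 - 0.343 = 0.082, the second is 0.745 × (0.565 - 0.490) = 0.056, and the total is 0.138.

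| p | Day 21: constant / combination only | Day 15: constant / combination only |
|---|---|---|
| 0.05 | 0.029 / 0.048 | 0.005 / 0.010 |
| 0.10 | 0.056 / 0.093 | 0.010 / 0.019 |
| 0.20 | 0.103 / 0.171 | 0.018 / 0.034 |
| 0.30 | 0.138 / 0.231 | 0.024 / 0.046 |
| 0.40 | 0.160 / 0.270 | 0.027 / 0.052 |

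**The case against.** The best defence is that the conflict is a leftover gloss. The definition applies to events in the DLT evaluation period, the next subsection is devoted to that period, and its arithmetic is sound: a start date, a count of five weeks, and an end at Week 3. Section 1.7.5.1 itself sends escalation decisions to the statistical section. On this view the 4-week wording was simply not updated. That is a plausible inference and a good reason to make 35 days the default. But no text I could read says which length governs (the flow chart and schema figures were not available to me), and it is the definition, not the observation-period text, that says what a DLT is.

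A second defence is oversight. The escalation hold, the weekly Phase I review and HROC control over opening the next cohort (section 6.3) make it unlikely that such an event goes unseen. This stands, but these safeguards do not say whether the event counts.

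A third is that the plan expects low toxicity (sections 1.4.10 and 4.1.8), so the disputed count may rarely arise. This is fair, and it is why the illustration starts at 5%. Table 7 lists rates of 20% to 40% as hypotheses, not expectations.

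A reader might go further in two ways that the documents do not support.

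- That the conflict also changes decisions at six patients. The Escalation Rules stop the procedure once six patients have been entered at a dose, so a different Table 6 entry there need not lead to a different next step.
- That the window's end floats with the ±7-day visit allowance. The observation-period text sets a period counted from a date and expressly lets it end without a visit under pembrolizumab.

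**Conclusion.** The inconsistency is real and is in the current text. On the literal reading it leaves a 7-day span, Days 15 to 21, in which a related Grade 3 or higher event is observed and delays escalation but does not meet the DLT definition. On the Day 15 reading the gap is about one day and the error lies mainly in the 5-week label. The observation-period text is ambiguous about its last day rather than self-contradictory.

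The consequence shown is at the first decision for a group of three, where one disputed event can move the action by one step. The percentages depend on assumed DLT rates and hazard shapes and only indicate scale. The case for correction rests on the two stated lengths in a rule that feeds the primary endpoint, and it should be corrected before the rule is applied further.

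**What to change.** State one window in protocol days wherever it appears. The default is Day -14 through Day 21 (35 days), which follows the dedicated subsection and its stated count.

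- Section 6.1, Definition of DLT: replace the 4-week parenthesis with *(Day -14 through Day 21)*.
- Section 1.7.5.1, Treatment Assignment: replace the 4-week follow-up with *from Day -14 through Day 21*.
- Section 6.1, DLT observation period: replace the end at Week 3 with *on Day 21*, and tie the escalation hold to that day.
- Section 6.1, Missing data: let the replacement rule refer to the same window.

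If the sponsor intended 4 weeks, remove the 5-week figure and give the fixed closing day in all three places. The second nivolumab dose would then normally fall at or beyond the end of the window, and the protocol should say so.

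Cost of the default: none in time if the hold already runs 35 days. Otherwise it adds 21 - 15 = 6 or 21 - 14 = 7 days of hold per group of three, and slightly more events may count as DLTs. A phone check of toxicity status on the closing day would help in the pembrolizumab cohorts, but it is an optional addition.

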### **DLT observation period**

There will be a 5-week evaluation period for observation of DLT during which time new subjects may be accrued within the same dose cohort, but dose escalation or de-escalation beyond the current dose cohort shall not be allowed. The date of reference for the 5 weeks is the first day of treatment including the lead-in period (Day -14); therefore the end of the DLT observation period occurs at Week 3. The end of the DLT observation period will not coincide with an office visit in the pembrolizumab cohorts; if no DLT has been reported by that time, the evaluation period will be considered to be passed.

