### **1.7.7 Dose Modifications and Withholding**

As toxicity of these agents is largely non-overlapping, management of toxicity is dependent on which agent is more likely to have resulted in the toxicity. Vertigo, somnolence, and circumoral paresthesia should be attributed to trigriluzole. Immune-related adverse events should be attributed to the anti- PD-1 antibody. Refer to agent-specific management instructions below for dose modifications and holdings.

*Overlapping toxicities of trigriluzole and anti- PD-1 antibody include fatigue, asthenia, nausea, dizziness, diarrhea, anorexia and liver injury. When these toxicities occur, both drugs should be held until toxicity resolves to grade 0-1.*

Study therapy (both agents) may be held for up to 6 consecutive weeks. Subjects who are not able to resume at least 1 study drug within a period of 6 weeks should be removed from the active treatment phase of the study and begin follow-up procedures.

Dosing interruptions are permitted in the case of medical / surgical events or logistical reasons not related to study therapy (e.g., elective surgery, unrelated medical events, patient vacation, and/or holidays). Missed doses should be omitted, not delayed. Subjects should be placed back on study therapy within 3 weeks of the scheduled interruption, unless otherwise discussed with the study PI or co-PI. The reason for interruption should be documented in the patient's study record. Tumor assessments should continue per the study calendar even if study medication was missed.

Delays due to holidays, weekends and bad weather will be permitted and will not be counted as a protocol violation, and efforts will be made to get the patient back on the original schedule so that assessments are uniform across subjects. If correlative samples are collected and the scheduled treatment that day is delayed/held for any reason, there is no need to re-collect correlative samples.

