**Trigriluzole + Pembrolizumab Study Calendar**

	Screening/ Baseline 	Treatment Week							
		Week -2	Week -1	Week 1	Week 4	Week 7	Q3 weeks (Weeks 10 – 109)	Q6 weeks  (Weeks 13 – 109)	Weeks 13, 25, 37, 49
Scheduling Window (Days):		Within 14 d	±3	±1	±7	±7	±7	±7	±7
Informed Consent	X								
Inclusion/Exclusion Criteria	X								
Demographics and Medical History, including BRAF status	X								
Prior and Concomitant Medication Review	X	X	X	X	X	X	X	X	X
Assess Baseline Symptoms/Adverse Events and Compliance	X	X	X	X	X	X	X	X	X
Vital Signs and Weight	X	X	X	X	X	X	X	X	X
ECOG Performance Status, Physical Examination	X	X		X	X	X		X	X
Routine Safety Laboratory Studies 	X	X 		X	X	X		X	X
Serum GGT	X			X		X			X
ECG 		X	X	X		X			X 
Trigriluzole Administration (PO continuous dosing)		X	X	X	X	X	X	X	X
Pembrolizumab Administration				X	X	X	X	X	X
Research Blood Collection for PK 		X		X		X			
Research Blood Collection for correlative science 	X			X		X			X 
Tumor Tissue Collection 	X			X		X			
Tumor Assessment 	X					X			X

Protocol Number: RCINJ# 051707

PI Name: [name]

Protocol Title: A Phase I Study to Evaluate the Safety of Trigriluzole (FC-4157/BHV-4157) in Combination with PD-1 Blocking Antibodies

49

RESERVED FOR IRB STAMP  
DO NOT MODIFY THIS SPACE

Form Version v120116

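### In the pembrolizumab cohorts no visit or laboratory test after the first infusion is guaranteed before a subject is scored as free of DLT

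*Combined protocol and SAP*

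**What the plan says.** Section 6.1, under the DLT observation period, states: "There will be a 5-week evaluation period for observation of DLT". The count starts on the first day of the lead-in (Day -14), and "the end of the DLT observation period occurs at Week 3". For the pembrolizumab cohorts it adds that "The end of the DLT observation period will not coincide with an office visit in the pembrolizumab cohorts", and that "if no DLT has been reported by that time, the evaluation period will be considered to be passed".

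Two other places give a different length. The definition of DLT in Section 6.1 covers toxicity that "occurred during the first 4 weeks of therapy", and Treatment Assignment in Section 1.7.5.1 also gives four weeks of follow-up for DLT.

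The "Trigriluzole + Pembrolizumab Study Calendar" in Section 1.10 schedules physical examination and routine safety laboratory tests at Week 1 and then at Week 4, with nothing between. The nivolumab calendar has both at Week 3.

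The text after Table 7 applies the same decision rules to pembrolizumab as to nivolumab. Section 1.7.7 says that the overlapping toxicities of trigriluzole and the antibodies "include fatigue, asthenia, nausea, dizziness, diarrhea, anorexia and liver injury".

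**The concern.** Cohort P1 is there to check whether the trigriluzole dose found with nivolumab is also tolerable with pembrolizumab. If it is not, the dose drops to Cohort P-1. That check is only as good as the observation behind each DLT count.

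Laboratory toxicity is a plausible DLT here. Section 1.4.2 reports dose-related transaminase elevation with riluzole. Section 1.4.8 lists liver function abnormalities among the most common laboratory findings with the PD-1 antibodies. A Grade 3 transaminase rise without symptoms is seen only if blood is drawn. If no draw on the combination is required before the subject is passed, the count can only be too low, and the error always favours passing the dose.

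**Working it through.** **1. When the period ends.** Section 1.7.6 says there is no Day 0. Days -14 to -1 are 14 days.
- Five weeks: 35 − 14 = 21, so the last day is Day 21, the end of Week 3. This reproduces the plan's statement.
- Four weeks: 28 − 14 = 14, so the last day is Day 14.

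**2. When subjects are seen.** Week w starts on Day 7(w − 1) + 1. The calendars allow ±7 days for Weeks 3 and 4.
- Pembrolizumab, Week 4: Day 22, permitted Days 15 to 29.
- Nivolumab, Week 3: Day 15, permitted Days 8 to 22.

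**3. Overlap of the first visit after the infusion visit with the DLT period.**

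| Period | Pembrolizumab Week 4: nominal date inside? | Permitted dates inside | Nivolumab Week 3: nominal date inside? | Permitted dates inside |
|---|---|---|---|---|
| 5 weeks (to Day 21) | No, 1 day late | 7 of 15 | Yes | 14 of 15 |
| 4 weeks (to Day 14) | No, 8 days late | 0 of 15 | No, 1 day late | 7 of 15 |

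If the boundary day were counted as inside, Day 22 would fall on the five-week boundary. The plan's own statement that the end does not coincide with a pembrolizumab visit rules out that reading.

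**4. What the Week 1 tests cover.** Section 4.1.8 says the antibody is given only after clinician and laboratory assessment. The Week 1 results therefore reflect the trigriluzole lead-in, not the combination.

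**5. Whether another rule closes the gap.** In Section 6.1 a subject is evaluable for toxicity after one dose of each drug. Subjects not evaluable for the whole period are replaced. Neither rule requires an assessment after the infusion.

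**6. Illustration, on assumptions only.** Let p be the true DLT rate and m the share of DLTs missed. Neither the rates nor the shares below come from the documents. The observed rate is q = p(1 − m), and for three subjects P(0 or 1 DLT) = (1 − q)³ + 3q(1 − q)². Recomputing the mTPI rule with target 0.30 and margins 0.05 (uniform prior assumed) gives stay at 1 of 3 and de-escalate at 2 of 3, so 0 or 1 means no de-escalation at that look.

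For p = 0.45:
- m = 0: q = 0.45; 0.166 + 0.408 = 0.575
- m = 0.25: q = 0.3375; 0.291 + 0.444 = 0.735
- m = 0.50: q = 0.225; 0.465 + 0.405 = 0.871

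| Assumed p | m = 0 | m = 0.25 | m = 0.50 |
|---|---|---|---|
| 0.40 | 0.648 | 0.784 | 0.896 |
| 0.45 | 0.575 | 0.735 | 0.871 |
| 0.50 | 0.500 | 0.684 | 0.844 |

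**The case against.** A reader might infer that laboratory DLTs on the combination cannot be detected, and that one found at Week 4 does not count. The documents support neither.

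- On the five-week reading the Week 4 visit may validly fall on Days 15 to 21. Calendar footnote 2 allows extra laboratory tests when clinically necessary, and subjects are told to call about side effects.
- The definition of DLT goes by when the toxicity occurred, not when it was found. No text excludes a Grade 3 result drawn on Day 22. Section 6.3 also provides for weekly review of toxicity and for oversight-committee review of DLTs.
- On the four-week reading the nominal nivolumab Week 3 visit is also one day late, so the contrast between the antibodies is weaker.
- The illustration treats a fixed share of DLTs as missed, and nothing in the documents supports any particular share. Asymptomatic Grade 3 amylase or lipase elevation is already exempt. Cohort P1 takes 3 to 6 patients, so 0 or 1 of 3 is not final acceptance.
- The mismatch is disclosed, and Section 1.3.1 expects the two antibodies to behave alike.

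All of this limits the wording and the numbers. It does not supply a required assessment. An early visit and an extra test are options, a call depends on symptoms, and review meetings can only see what has been measured. The expected similarity of the antibodies is what P1 is meant to check.

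**Conclusion.** The point stands in this form: on either stated length, no visit or laboratory test after the first pembrolizumab infusion is guaranteed inside the DLT period, yet a subject with no reported DLT is passed. How a qualifying abnormality first found at Week 4 is classified is left unspecified.

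The same decision rules are thus applied with less ascertainment in P1 and P-1 than in the nivolumab cohorts. The contrast is clear on the five-week reading. On the four-week reading it is narrower (0 against 7 of 15 permitted dates). The direction favours passing the dose.

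The size cannot be derived from the documents. The rise from 57% to 74% at an assumed 45% DLT rate, with a quarter of DLTs missed, shows only how sensitive the first look at three subjects is. It is neither an estimate for this trial nor the probability that the dose is finally accepted. This is a worthwhile correction because the remedy uses a visit that is already scheduled.

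**What to change.** 1. Reconcile the four-week period (Section 1.7.5.1 and the definition of DLT) with the five-week period (DLT observation period), so that one length applies throughout.
2. For Cohorts P1 and P-1, replace the default-pass sentence. A subject counts as DLT-free only after the scheduled Week 4 assessment and laboratory results, obtained before the second infusion, have been reviewed. The period closes no earlier than the reconciled length, so an early Week 4 visit cannot shorten it.
3. State that a qualifying toxicity found at that assessment counts as a DLT.

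The cost is protocol wording and a short wait before each cohort decision. On the five-week reading this is 22 − 21 = 1 day at the nominal date and up to 29 − 21 = 8 days with the visit window. On the four-week reading it is 22 − 14 = 8 days and up to 29 − 14 = 15 days. Follow-up for DLT becomes slightly longer than in the nivolumab cohorts. No visit or test is added.
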